8.2.9.1. Bleeding and Bruising Assessment

The presence of visible bleeding or bruising at the injection site will be recorded on the eCRF as applicable and will be recorded as an AE if judged to be more severe than expected with a typical SC administration.

A bandage may be placed on the injection site after assessment.

8.3. Adverse Events, Serious Adverse Events, and Product Complaints

The definitions of AEs, SAEs, and PCs can be found in Section 10.3.

These events will be reported by the participant, or, when appropriate, by a caregiver, surrogate, or the participant's legally authorized representative.

The investigator and any qualified designees are responsible for detecting, documenting, and recording events that meet these definitions and remain responsible for following up events that are serious, considered related to the study intervention or study procedures, or that caused the participant to discontinue the study as described in Section 7.

Care will be taken not to introduce bias when detecting events. Open-ended and non-leading verbal questioning of the participant is the preferred method to inquire about event occurrences.

After the initial report, the investigator is required to proactively follow each participant at subsequent visits or contacts. All SAEs and AEs of special interest as defined in Section 8.3.3 will be followed until resolution, stabilization, the event is otherwise explained, or the participant is lost to follow-up as defined in Section 7.3.

For PCs, the investigator is responsible for ensuring that follow-up includes any supplemental investigations as indicated to elucidate the nature or causality. Further information on follow-up procedures is provided in Section 10.3.

8.3.1. Timing and Mechanism for Collecting Events

This table describes the timing, deadlines, and mechanism for collecting events.

Event	Collection Start	Collection Stop	Timing for Reporting to Sponsor or Designee	Mechanism for Reporting	Back-up Method of Reporting
Adverse Event					
AE	Signing of the ICF	Participation in study has ended	As soon as possible upon site awareness	AE CRF	N/A
Serious Adverse Event					
SAE and SAE updates – prior to start of study intervention and deemed reasonably possibly related to study procedures	Signing of the ICF	Start of intervention	Within 24 hours of awareness	SAE paper form	N/A
SAE and SAE updates – after start of study intervention	Start of intervention	Participation in study has ended	Within 24 hours of awareness	SAE paper form	N/A
SAE* – after participant's study participation has ended and the investigator becomes aware	After participant's study participation has ended	N/A	Promptly	SAE paper form	N/A

Event	Collection Start	Collection Stop	Timing for Reporting to Sponsor or Designee	Mechanism for Reporting	Back-up Method of Reporting
Pregnancy					
Pregnancy in participants and partners of participants	After the start of study intervention	Day 71 (± 3 days) or upon early discontinuation	Within 24 hours (see Section 8.3.2)	Pregnancy paper form	N/A
Product Complaints					
PC associated with an SAE or might have led to an SAE	Start of study intervention	End of study intervention	Within 24 hours of awareness	Product Complaint form	N/A
PC not associated with an SAE	Start of study intervention	End of study intervention	Within 1 business day of awareness	Product Complaint form	N/A
Updated PC information	—	—	As soon as possible upon site awareness	Originally completed Product Complaint form with all changes signed and dated by the investigator	N/A
PC (if investigator becomes aware)	Participation in study has ended	N/A	Promptly	Product Complaint form	-

* SAEs should not be reported unless the investigator deems them to be possibly related to study treatment or study participation.

8.3.2. Collection of Pregnancy Information

8.3.2.1. Participants Who Become Pregnant

The investigator will collect pregnancy information on any participant who becomes pregnant while participating in this study. The initial information will be recorded on the appropriate form and submitted to the sponsor within 24 hours of learning of a participant's pregnancy.

The participant will be followed to determine the outcome of the pregnancy. The investigator will collect follow-up information on the participant and the neonate and the information will be forwarded to the sponsor. Generally, follow-up will not be required for longer than 6 to 8 weeks beyond the estimated delivery date. Any termination of pregnancy will be reported, regardless of gestational age, fetal status, presence or absence of anomalies, or indication for the procedure.

While pregnancy itself is not considered to be an AE or SAE, any pregnancy complication or elective termination of a pregnancy for medical reasons will be reported as an AE or SAE.

A spontaneous abortion (occurring at <20 weeks gestational age) or still birth (occurring at ≥ 20 weeks gestational age) is always considered to be an SAE and will be reported as such.

Any post-study pregnancy-related SAE considered reasonably related to the study intervention by the investigator will be reported to the sponsor as described in Section 8.3.1. While the investigator is not obligated to actively seek this information in former study participants, the investigator may learn of an SAE through spontaneous reporting.

Any participant who becomes pregnant while participating in the study may be withdrawn from the study. If the participant is discontinued from the study, follow the standard discontinuation process and continue directly to the follow-up phase. The follow-up on the pregnancy outcome should continue independent of intervention or study discontinuation.

8.3.2.2. Participants With Partners Who Become Pregnant

When to collect pregnancy information

In most circumstances, the investigator will attempt to collect pregnancy information from a participant's partner who becomes pregnant while the participant is in this study.

After learning about a pregnancy in the partner of a study participant, the investigator

- will obtain a consent to release information from the pregnant partner directly, and
- within 24 hours after obtaining this consent will record pregnancy information on the appropriate form and submit it to the sponsor.

The partner will be followed to determine the outcome of the pregnancy. Information on the status of the mother and neonate will be forwarded to the sponsor. Generally, the follow-up will be no longer than 6 to 8 weeks after the estimated delivery date. Any termination of the pregnancy will be reported regardless of gestational age, fetal status, presence or absence of anomalies, or indication for the procedure.

When not to collect pregnancy information

It is not necessary to collect information about a pregnancy in the partner of a study participant in these circumstances:

- the partner of the study participant was not exposed to the study intervention, or
- the participant did not contribute the sperm or ova that resulted in the pregnancy.

8.3.3. Adverse Events of Special Interest

AEs of special interest for this program include:

- infection and
- systemic allergic/hypersensitivity reactions.

If infections or allergic/hypersensitivity reactions are reported, site staff will provide details on these events as instructed on the eCRF. A PK and hypersensitivity cytokine panel will be collected, as detailed in Section 10.2.2, when possible, for any participant who experiences an AE of systemic allergic/hypersensitivity reaction during the study.

8.4. Pharmacokinetics

At the visits and times specified in the SoA in Section 1.3, venous blood samples will be collected from all participants to determine the serum concentrations of mirikizumab. Samples will be analyzed at a laboratory approved by the sponsor and stored at a facility designated by the sponsor. Concentrations of mirikizumab will be assayed using a validated bioanalytical assay.

A maximum of 3 samples may be collected at additional time points during the study if warranted and agreed upon between the investigator and the sponsor. The timing of sampling may be altered during the course of the study based on newly available data to ensure appropriate monitoring.

Instructions for the collection and handling of blood samples will be provided by the sponsor.

The actual date and time (24-hour clock time) of each sample must be recorded.

Further details on sample retention are described in Section 10.1.11.

8.5. Pharmacodynamics

Pharmacodynamic parameters are not evaluated in this study.

8.6. Genetics

A blood sample for DNA isolation will be collected from participants.

See Section 10.5 for information regarding genetic research and Section 10.1.11 for details about sample retention and custody.

8.7. Biomarkers

Biomarkers are not evaluated in this study.

8.8. Immunogenicity Assessments

Immunogenicity is not evaluated in this study.

8.9. Health Economics or Medical Resource Utilization and Health Economics

Health economics or medical resource utilization and health economics parameters are not evaluated in this study.

9. Statistical Considerations

The statistical analysis plan will be finalized prior to first participant first visit, and it will include a more technical and detailed description of the statistical analyses described in this section. This section is a summary of the planned statistical analyses of the most important endpoints, including primary and secondary endpoints.

9.1. Statistical Hypothesis

The primary objective of this study is to evaluate the bioequivalence of a single 2-mL SC dose of citrate-free mirikizumab solution in AI compared to 2 × 1-mL SC doses of citrate-free mirikizumab solution in AI.

9.2. Analyses Sets

Participant Analysis Set	Description
Enrolled	All participants randomly assigned to study intervention.
Safety analysis set	All participants who are exposed to study intervention. Participants will be analyzed according to the intervention they actually received.
PK analysis set	All enrolled participants who receive a dose of study intervention and have evaluable PK data according to the study intervention actually received.

Participants may be excluded from the PK analysis set in the event of

- a device malfunction
- administration of only 1 of the 2 × 1-mL AI doses, or
- administration of an incorrect or incomplete dose.

9.3. Statistical Analyses

Statistical analysis of this study will be the responsibility of the sponsor or designee.

Safety analyses will be conducted for all enrolled participants who were administered study intervention, whether or not they completed all protocol requirements.

Additional exploratory analyses of the data will be conducted as appropriate. Study results may be pooled with the results of other studies for safety and population PK analysis purposes, for totality of evidence.

9.3.1. General Considerations

Handling of missing, unused, and spurious data is addressed prospectively in the overall statistical methods described in the protocol and in the statistical analysis plan, where appropriate. Adjustments to the planned analyses will be described in the final clinical study report.

9.3.2. Primary Endpoint Analysis

9.3.2.1. Pharmacokinetic Parameter Estimation

Pharmacokinetic parameter estimates for mirikizumab will be calculated using standard noncompartmental methods of analysis.

The primary parameters for analysis will be the C_{max} , $AUC(0-\infty)$, and $AUC(0-t_{last})$ of mirikizumab. The secondary parameter for analysis will be the t_{max} of mirikizumab. Other noncompartmental parameters, such as half-life associated with the terminal rate constant, apparent clearance, and apparent volume of distribution, may be reported.

9.3.2.2. Pharmacokinetic Statistical Inference

The C_{max} , $AUC(0-\infty)$, and $AUC(0-t_{last})$ will be log-transformed and analyzed using a linear fixed-effects model. The model will include mirikizumab administration method ($2 \times 1\text{-mL SC}$ injections of 100 mg/mL citrate-free mirikizumab as reference, and $1 \times 2\text{-mL SC}$ injections of 100 mg/mL citrate-free mirikizumab as test), injection location, and weight category stratification as fixed effects. The administration method differences will be back-transformed to present the ratios of geometric least squares means and the corresponding 90% CI. Comparisons will be made between the 2 administration methods.

The 2 administration methods will be considered bioequivalent if the 90% CIs of the ratio of geometric least squares means fall within 0.80 to 1.25.

In addition, the t_{max} of mirikizumab between the administration methods will be analyzed using a Wilcoxon rank sum test. Estimates of the median difference, approximately 90% CIs, and p-values from the Wilcoxon rank sum test will be calculated.

Additional PK analyses may be conducted if deemed appropriate.

9.3.3. Secondary Endpoint Analysis

9.3.3.1. Clinical Evaluation of Safety

All investigational product and protocol procedure AEs and PCs will be listed, and if the frequency of events allows, safety data will be summarized using descriptive methodology.

A TEAE is defined as an AE which occurs postdose or which is present prior to dosing and becomes more severe postdose. The incidence of TEAEs for each treatment will be presented by severity and by association with investigational product as perceived by the investigator. AEs reported to occur prior to study entry will be distinguished from those reported as new or increased in severity during the study. Each AE will be classified by the most suitable term from the medical regulatory dictionary.

The number of SAEs will be reported.

9.3.3.2. Statistical Evaluation of Safety

Safety parameters that will be assessed include clinical laboratory parameters and vital signs. The parameters and changes from baseline (predose), where appropriate, may be listed and

summarized using standard descriptive statistics. Additional analysis will be performed if warranted upon review of the data.

9.3.4. Exploratory Endpoint Analysis

9.3.4.1. Pharmacokinetic Parameter Estimation – Injection-site Location

See Section 9.3.2.1. Additional exploratory analyses may be conducted, and the details will be included in the statistical analysis plan.

9.3.5. Other Safety Analyses

9.3.5.1. Injection-site Assessments

If available, any incidence of erythema, induration, pain, pruritus, edema, bleeding, and bruising will be listed.

9.4. Interim Analysis

No interim analyses are planned for this study. If an unplanned interim analysis is deemed necessary for reasons other than a safety concern, the protocol must be amended.

9.5. Sample Size Determination

Approximately 484 participants, approximately 242 participants in each treatment arm, may be enrolled so that approximately 400 participants, 200 in each test and reference group, complete the study.

Within each weight category, participants will be assigned to an SC injection site of either the arm, thigh, or abdomen, approximately 80 participants per injection site for the reference and test arms.

A sample size of 200 participants per treatment group will provide approximately 90% probability that the 90% CI of the geometric mean ratio of C_{max} and AUC between groups will fall within the equivalence boundary of 0.80 to 1.25. This sample size calculation was based on the assumptions that the coefficient of variation of PK parameters is up to 41.8% for each treatment group and the expected ratio of geometric means is between 0.9 and 1.1.

10. Supporting Documentation and Operational Considerations

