4.3.2.1. Pharmacokinetic Statistical Methodology

The C_{\max} , $AUC_{(0-\infty)}$, and $AUC_{(0-t_{\text{last}})}$ will be log-transformed and analyzed using a linear fixed-effects model. The model will include mirikizumab administration method ($2 \times 1 \text{ mL}$ as reference, $1 \times 2 \text{ mL}$ as test), injection site location, and weight category stratification as fixed effects. The least squares (LS) mean differences between mirikizumab administration method administrations (across all locations) will be back transformed to present the ratios of geometric LS means and the corresponding 90% confidence interval (CI). Comparisons will be made between the 2 administration methods.

Example SAS Code:

```
proc mixed data=xxxx;  
by parameter;  
class administration location strat_weight;  
model log_pk = administration location strat_weight / residual;  
lsmeans administration / alpha=0.1 cl pdiff;
```

```
lsmeans location / alpha=0.1 cl pdiff;
ods output lsmeans=lsmeans diffs=diffs;
run;
```

The two administration methods will be considered bioequivalent if the 90% CIs of the ratio of geometric LS means fall within 0.800 to 1.250.

In addition, the t_{max} of mirikizumab between the two administration methods will be analyzed using a Wilcoxon rank-sum test. Estimates of the median, the median difference, approximately 90% CIs, and p-values from the Wilcoxon rank-sum test will be reported.

Example SAS code:

```
proc nparlway data = xxx hl(refclass="xx") alpha = 0.1;
by parameter;
class administration;
var pk;
exact wilcoxon hl;
ods output wilcoxontest = Wilcoxon;
ods output HodgesLehmann=hl;
run;
```

Using the same model, the following exploratory comparisons will also be made:

- The 2 administration methods (2×1 mL [Reference] versus 1×2 mL [Test]) compared separately at each injection location (injection location will be removed from the model above)
- The 3 injection locations (arm [Test] versus abdomen [Reference] and thigh [Test] versus abdomen [Reference]) separately for each administration method (2×1 mL [Reference] versus 1×2 mL [Test]) (administration methods will be removed from the model above)

There is no intention for formal statistical analysis in these comparisons but rather to explore potential heterogeneity; therefore, bioequivalence will not be determined based on this exploratory purpose.

Additional PK analyses may be conducted if deemed appropriate.

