4.6. Changes from the Protocol-Specified Statistical Analyses

There were no changes from the protocol-specified statistical analyses.

5. Sample Size Determination

Approximately 440 participants, 220 participants in each treatment arm, may be enrolled so that approximately 400 participants, 200 in each test and reference group, complete the study.

Within each weight category, participants will be assigned to an SC injection site of either the arm, thigh, or abdomen, approximately 73 participants per injection site for the reference and test arms.

A sample size of 200 participants per treatment group will provide approximately 90% probability that the 90% CI of the geometric mean ratio of C_{max} and area under the concentration versus time curve between groups will fall within the equivalence boundary of 0.80 to 1.25. This sample size calculation was based on the assumptions that the coefficient of variation of PK parameters is up to 41.8% for each treatment group and the expected ratio of geometric means is between 0.9 and 1.1.

6. Data Presentation

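### Does the stated power of about 90% overstate the chance that all three primary PK parameters pass?

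*Protocol*

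**What the plan says.** Protocol 9.5 bases power on completers: "A sample size of 200 participants per treatment group", it says, "will provide approximately 90% probability that the 90% CI of the geometric mean ratio of C_{max} and AUC between groups" lies inside the limits. The assumptions are a CV of at most 41.8% in each group and that "the expected ratio of geometric means is between 0.9 and 1.1". SAP section 5 carries the same statement: "A sample size of 200 participants per treatment group will provide approximately 90% probability that the 90% CI of the geometric mean ratio".

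Protocol 9.3.2.1 and SAP 4.3.2 name three primary parameters: Cmax, AUC(0-∞) and AUC(0-tlast). Under Protocol 9.3.2.2 the two methods "will be considered bioequivalent if the 90% CIs of the ratio of geometric least squares means fall within 0.80 to 1.25". SAP 4.3.2.1 has the same rule: "The two administration methods will be considered bioequivalent if the 90% CIs of the ratio of geometric LS means fall within 0.800 to 1.250".

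Neither document gives a correlation between the parameters, a separate CV for each, or a probability that all three pass.

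**The concern.** The power sentence mentions Cmax and AUC together and gives one figure. The decision rule uses the plural, and no text says that one parameter is enough, so success means that all three intervals lie inside the limits. Three requirements that are each met with probability 90% are met together with a lower probability, unless they are almost perfectly correlated. A reader who takes 90% as the chance of a successful study would then be too optimistic. The stake is the sponsor's risk that a device which is in fact bioequivalent fails. The risk of a false declaration does not rise, because requiring three passes can only make a declaration harder.

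**Working it through.** **Inputs from the documents.** 200 per group; CV 41.8% (the stated ceiling); limits 0.80 to 1.25; true ratio 0.9 to 1.1 (all Protocol 9.5). A 90% CI inside the limits is two one-sided tests at 5% each.

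**The plan's own figure, one parameter.**

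- Log-scale SD = √ln(1 + 0.418²) = 0.4013.
- SE of the log ratio = 0.4013 × √(2/200) = 0.0401.
- At ratio 0.90 the distance to the lower limit is ln(0.90/0.80) = 0.1178, or 2.935 SE. The distance to the upper limit is ln(1.25/0.90) = 0.3285, about 8 SE, so that side does not matter.
- Normal approximation: Φ(2.935 − 1.645) = Φ(1.290) = 90.15%.
- Integrating over the variance estimate: 90.07%. With 199 per group it is 89.94%.

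The stated 90% is therefore single-parameter power at ratio 0.90, and 200 is the smallest group size that delivers it. At other ratios one parameter has 99.57% (0.95), 99.99% (1.00) and 93.76% (1.10).

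**All three parameters.** The joint figure needs correlations, which are assumptions here. The AUC–AUC correlation should be very high. Half-life is about 9.3 days (Protocol 2.2.4) and the last sample is on Day 71, 70 days after dosing: 70/9.3 = 7.5 half-lives. A remainder of roughly 2^(−7.5), about 0.5%, leaves AUC(0-∞) and AUC(0-tlast) almost the same variable. A value of 0.995 is used below, with a more pessimistic last column. Joint power was simulated with correlated estimates and correlated variances, 200,000 draws per cell and 394 degrees of freedom, requiring all three CIs inside the limits.

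| Scenario, 200 per group | Cmax–AUC 0.8 | 0.9 | 0.95 | Cmax–AUC 0.5, AUC–AUC 0.97 |
|---|---|---|---|---|
| All CV 41.8%, all ratios 0.90 | 85% | 87% | 88% | 82% |
| All CV 41.8%, all ratios 0.915 | 93% | 94% | 94% | 91% |
| All CV 41.8%, all ratios 0.95 | 99% | 99% | 99% | 99% |
| All CV 41.8%, all ratios 1.09 | 94% | 94% | 95% | 92% |
| All CV 41.8%, all ratios 1.10 | 90% | 91% | 92% | 88% |
| All CV 41.8%, Cmax 0.90, both AUCs 0.95 | 90% | 90% | 90% | 90% |
| Cmax CV 41.8%, AUC CV 36%, all ratios 0.90 | 89% | 89% | 90% | 87% |
| All CV 38%, all ratios 0.90 | 91% | 92% | 92% | 89% |

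Independence would give 0.9007³ = 73% in the first row, but exposure measures from one concentration profile are not independent. With all correlations at 0.99 the first row is 88.5%.

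**The case for a change.** The strongest case for acting is that ratio 0.90 with CV 41.8% is the sponsor's own planning limit, and the only point in the stated range where the calculation returns the stated 90%. At that point the direction of the gap does not depend on the assumed correlations: the joint figure is lower unless correlation is almost perfect. The chance of failure would be about 12% to 15%, against the 10% a reader might infer. Enrolling 242 per arm is no answer, since Protocol 9.5 presents that number as an allowance so that 200 complete. Writing that all three CIs must pass would also settle a mixed result in advance, which has some value in an open-label study. And SAP section 5 still carries enrolment of 440, so it could be edited at the same time.

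The arithmetic in this case stands. What does not stand is that the plan promises something it fails to deliver. The power sentence speaks of one CI, in the singular, and its figure is exact on that reading. The corner needs all three parameters at the maximum CV and at the same extreme ratio. On the decision rule, a plural applied to three named primary parameters already means each of them, and neither document offers another rule. A mixed result would be read as not bioequivalent without any added word. Whether 41.8% is total or residual CV is also unstated, but if it is total, adjustment for weight category and injection site would raise power.

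**Conclusion.** The concern does not call for a change. The stated 90% is right as per-parameter power at ratio 0.90 and CV 41.8%. The unstated joint probability falls short by about 2 to 5 points when all three parameters sit at that corner (85% to 88%, for an assumed Cmax–AUC correlation of 0.8 to 0.95 and AUC–AUC of 0.995 to 0.999), and by about 8 points at the least favourable correlations tabulated. Elsewhere in the planning range it is about 90% or higher under the main assumptions, dipping to about 89% when only the AUC CV is lower and all ratios stay at 0.90. These sizes are assumption-based, because the documents give neither correlations nor separate CVs.

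What is missing is a label and a supplementary figure. The sponsor could add both, using the correlation in its own earlier mirikizumab data, but the group size, model, limits and conclusion drawn from the study would be the same.
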